11. SAFETY

The following analyses will be performed on the FAS.

11.1. Study duration

Study duration will be calculated according to the formula below:

$$\text{Study duration (days)} = \text{Reference End Date} - \text{Reference Start Date} + 1$$

It will be described (see §6.2) on the FAS.

11.2. Incidents and expected side effects

For safety analyses, only incidents and expected side effects are considered, i.e. adverse events with a relationship to study device other than “not related”.

- Summary of incidents

A summary table will be produced:

- number and percentage of subjects with at least one incident;
- number and percentage of subjects with at least one incident leading to definitive study device discontinuation;
- number and percentage of subjects with at least one serious incident.

The number of incidents of each category will also be provided in this table.

- Analysis of incident

The number and percentage of subjects with incidents will be summarised by System Organ Class and Preferred term.

The number of incidents of each category will also be provided in this table.

A listing of serious incidents will be provided if applicable.

All incidents leading to definitive discontinuation of the trial device will be listed if applicable.

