- **Safety:** All adverse events and incidents will be listed, but only treatmentemergent adverse events/incidents (non-serious + serious)/ undesirable expected side effects will be summarized.

Two groups (called treatment groups) will be extracted from the cohort according to the treatment chosen by the patient.

Adverse events and incidents will be summarized by the number and percentage of patients (by treatment group), classified by System Organ Class and Preferred Term as defined by MedDRA dictionary.

For a given treatment group, a given adverse event will be counted treatment emergent only once per patient during the treatment period.

Frequency and percentage of patients with at least one reported adverse event/ incident/ expected side effect will be tabulated by System Organ Class and by treatment group.

Version: **2.0**; **08** Sep **2021** Page **19** of **61** Study Number: **LPH-2101**

3. Flow Chart

	ACUTE PHASE			FOLLOW-UP			
Visit name	Screening/Inclusion	At home	Telephone call	End of treatment	At home	Telephone call	End of study
Visit Number	V1		TC1	V2		TC2	V3
Days/Weeks	D1	D1 – D10	D5±2	D10±2	D11 – D30±5	D20±2	D30 ± 5
Screening and General Assessments							
Information and consent process	Х						
Eligibility criteria	Х						
Demography and Medical history	Х						
Physical and clinical examination	X			Х			Х
Ongoing medication	Х						
Patient's choice for using Healsea® Children self-administration or not	Х						
Treatment							
Acute phase (Healsea® Children or no saline irrigation as add on therapy)		Х					
Assessments							
Subject e-diary (WURSS-K)		Х			X*		
Adverse Events/incidents/undesirable expected side effects and concomitant medication reporting	Х	Х	Х	Х	х	х	Х

^{*} After D10, the WURSS-K will be assessed once daily until the subject feels not sick for two consecutive days if applicable.

Version: **2.0; 08 Sep 2021** Study Number: **LPH-2101**

4. Identification and description of the investigational Device

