9.5 Safety

All adverse events/incidents/expected side effects will be listed, but only treatment-emergent adverse events/incidents (non-serious + serious) will be summarized.

Two groups (called treatment groups) will be extracted from the cohort according to the treatment chosen by the patient.

Page **39** of **61** Version: 2.0; 08 Sep 2021

Adverse events/incidents/expected side effects will be summarized by the number and percentage of patients (by treatment group), classified by System Organ Class and Preferred Term as defined by MedDRA dictionary.

For a given treatment group, a given adverse event will be counted treatment emergent only once per patient during the treatment period.

Frequency and percentage of patients with at least one reported adverse event/incident / expected side effects will be tabulated by System Organ Class and by treatment group.

10. Data management

Subject data will be entered into an electronic case report form.

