15.1 Definitions

Incident means any malfunction or deterioration in the characteristics or performance of a device made available on the market, including use-error due to ergonomic features, as well as any inadequacy in the information supplied by the manufacturer and any undesirable side-effect (MDR 2017/745).

Serious incident means any incident that directly or indirectly led, might have led or might lead to any of the following: (a) the death of a patient, user or other person, (b) the temporary or permanent serious deterioration of a patient's, user's or other person's state of health, (c) a serious public health threat (MDR 2017/745).

Serious public health threat means an event which could result in imminent risk of death, serious deterioration in a person's state of health, or serious illness, that may require prompt remedial action, and that may cause significant morbidity or mortality in humans, or that is unusual or unexpected for the given place and time (MDR 2017/745).

Expected and foreseeable side effects (MEDDEV 2 12-1 rev. 8)

They meet all the following criteria:

- Clearly identified in the manufacturer's labelling,
- Clinically well known as being foreseeable and having a certain qualitative and quantitative predictability when the device is used and performs as intended,
- Documented in the device master record, with an appropriate risk assessment, prior to the occurrence of the incident and,
- Clinically acceptable in terms of the individual patient benefit.

Adverse event means any untoward medical occurrence, unintended disease or injury or any untoward clinical signs, including an abnormal laboratory finding, in subjects, users or other persons, in the context of a clinical investigation, whether related or not related to the investigational device (MDR 2017/745).

Adverse or intercurrent events are graded as follows:

Mild: Awareness of signs or symptoms but easily tolerated.

Moderate: Uncomfortable enough to cause interference with usual activity.

Severe: Incapacity with inability to work or do usual activity.

Page **48** of **61** Version: 2.0; 08 Sep 2021

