10.4. Non-related adverse events

In the following paragraph, for a smoother reading:

- adverse events will be referred as AE;
- treatment-emergent adverse events will be referred as TEAE.

Adverse events are coded using the MedDRA dictionary version 20.1. They are classified by System Organ Class and Preferred Term.

For efficacy analyses, only non-related AEs are considered, i.e. adverse events with a relationship to study device equal to “not related”. These analyses will be performed on the FAS.

An adverse event will be considered as a treatment-emergent adverse event (TEAE) if:

- it was reported at least one day after screening, or at least two days after screening in the case of the AE “rhinitis”;
- it was not present prior to the reference start date;
- it was present prior to the reference start date and worsened during the study (increase of intensity);
- it reappears after the reference start date (finished before the reference start date).

Missing or incomplete dates will be estimated as described in §6.4.4 in order to determine the TEAEs, but they will be presented as reported in CRF in the data listings. Generally, an adverse event for which the onset date is missing or incomplete and does not permit to identify the onset according to the date of the reference start date (i.e. missing onset day and month/year corresponding to the reference start date) will be considered as treatment-emergent.

Note: if the intensity/severity is missing, a conservative approach will be adopted and the intensity/severity will be considered as severe.

A given treatment-emergent adverse event (according to the MedDRA terminology) will be counted only once per subject. If a subject experienced several AEs in the same SOC/PT, the most severe intensity will be retained for this SOC/PT.

- Summary of non-related adverse events

A summary table will be produced:

- number and percentage of subjects with at least one non-related adverse event (AE);
- number and percentage of subjects with at least one non-related AE leading to definitive study device discontinuation;
- number and percentage of subjects with at least one non-related TEAE.

The number of non-related AEs of each category will also be provided in this table.

- Analysis of non-related treatment-emergent adverse event

The number and percentage of subjects with non-related TEAEs will be summarised by System Organ Class and Preferred term.

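### The SAP splits adverse events by relationship to the device, plans no by-group table of all of them as protocol 9.5 does, and does not declare the change

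*SAP*

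**What the plan says.** **Protocol.** Section 9.5 lists every event and then states that "only treatment-emergent adverse events/incidents (non-serious + serious) will be summarized". The summaries are by treatment group, System Organ Class (SOC) and Preferred Term (PT). It adds that "Frequency and percentage of patients with at least one reported adverse event/incident / expected side effects will be tabulated" by SOC and treatment group. The synopsis gives the same plan. Neither place filters on causality, and section 15.1 defines an adverse event as an untoward occurrence "whether related or not related to the investigational device".

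**SAP.** The events are divided by their recorded relationship to the device.

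- Section 10.4, under Efficacy: "For efficacy analyses, only non-related AEs are considered". Its summary table has three rows: any non-related event, any leading to definitive device discontinuation, and the "number and percentage of subjects with at least one non-related TEAE".
- Section 11.2, under Safety: "For safety analyses, only incidents and expected side effects are considered", defined as events with a relationship other than not related. Its three rows are any incident, any leading to device discontinuation, and the "number and percentage of subjects with at least one serious incident".
- Section 12 declares one change from the protocol, the definition of symptom duration.
- Section 13.1 lists one output that holds all events together: Listing 16.2.7.1, a subject listing.

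**The concern.** The hypothesis in protocol 7.1 is that the spray adds efficacy without raising safety concerns, and protocol 7.3 makes safety an objective. The natural display for that is how many children in each group had any treatment-emergent event, which is what protocol 9.5 plans.

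Under the SAP, the Safety section shows only events that someone has linked to the device. Children on conventional therapy do not use it (protocol 8.2), so their events would be expected to be classed almost entirely as not related and to appear under Efficacy. A Healsea child's event can go to either section, depending on a causality judgement made with the treatment known. The two displays therefore do not compare the groups like for like, and a reader cannot put them together to make that comparison.

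**Working it through.** **1. Planned by-group adverse event tables (SAP 13.1, checked against the mocks in 13.2).**

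| Table | SAP section | Events covered |
|---|---|---|
| 14.2.4.1.1 | Efficacy | Non-related, summary |
| 14.2.4.1.2 | Efficacy | Non-related treatment-emergent, by SOC/PT |
| 14.3.1.1 | Safety | Incidents, summary |
| 14.3.1.2 | Safety | Related treatment-emergent, by SOC/PT (the mock is titled only as incidents) |

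That makes 2 + 2 = 4 tables, of which 0 cover all events. The mocks add no combined table.

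**2. Can patients with any event be recovered?** In one group of n children, let a have a non-related event and b a related one, with the same treatment-emergent rule applied to both. A child can be in both counts, so

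max(a, b) ≤ patients with any event ≤ min(n, a + b).

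While a + b ≤ n, the width of this interval is min(a, b), the smaller of the two table counts.

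**3. Illustration.** The documents give no adverse event rates, so these counts are assumed: n = 100 per group, a = 30 in each group, and b = 3, 6 or 9 in the Healsea group.

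| Healsea b | Healsea, any event | Difference if controls have 0 incidents (any event = 30) | Difference if controls have 1 incident (any event = 30–31) |
|---|---|---|---|
| 3 | 30–33 | 0 to +3 points | −1 to +3 points |
| 6 | 30–36 | 0 to +6 points | −1 to +6 points |
| 9 | 30–39 | 0 to +9 points | −1 to +9 points |

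**4. Can event counts be added instead?** Not securely at SOC/PT level. SAP 10.4 states a treatment-emergent rule for the non-related table, while SAP 11.2 states none for incidents. The title of Table 14.3.1.2 in the list implies such a filter; the corresponding mock title does not. If incidents are counted without the filter, the two SOC/PT tables do not use the same definition. The lower bound max(a, b) for treatment-emergent events is then also not guaranteed where b exceeds a.

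**5. Serious events.** The two summaries have 3 + 3 = 6 rows. One concerns serious events, and it is limited to incidents. The mock listing of non-related events has a seriousness column, but that listing covers only events leading to device discontinuation. A serious event judged not related, without discontinuation, is identifiable only in the full subject listing.

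**The case against.** **The protocol may not intend one combined table.** It never uses a word such as pooled, and the slashes in 9.5 could denote separate categories. This stands as an ambiguity but does not remove the point. Even as a separate category, adverse event covers related and unrelated events under protocol 15.1, and no SAP table shows that category by group.

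**Protocol 9.1 leaves details to the SAP.** It does, and two complementary tables could be called presentation. But restricting the safety analyses by causality and moving the remaining events to Efficacy changes what the planned summary contains. SAP section 12 is the place to declare that.

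**Incident tables have their own basis.** For this CE-marked device, protocol section 15 is built around incidents and expected side effects, and the objective in 7.3 concerns tolerance of the device. This stands in full: the incident tables should stay. They do not replace the summary in 9.5.

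**Stronger inferences that a reader might draw.**

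- *Safety data are dropped.* They are not: both halves are tabulated by group and Listing 16.2.7.1 holds every event.
- *The Safety tables have no control group.* The mocks have a conventional-therapy column. That it will be nearly empty is an expectation, and the documents give no rule for assigning relationship in children who do not use the device.
- *The protocol requires a by-group table of serious adverse events.* It does not clearly do so. The serious/non-serious wording in 9.5 can be read as qualifying incidents only, and 15.1 defines a serious incident but not a serious adverse event.
- *The split was chosen after seeing the data.* Section 12 shows that diary responses had been seen when it was written, but nothing links that to the adverse event split.

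**Conclusion.** The point holds as a gap in reporting. The SAP replaces a causality-free by-group summary with two subsets, none of its 4 by-group tables covers all events, and the change is undeclared. The number of children with any treatment-emergent event, which protocol 9.5 plans to report, cannot be obtained from the planned tables.

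The table count comes directly from the documents. The patient-count uncertainty equals the smaller of the two table counts and depends on both using the same treatment-emergent rule; the figures of 3, 6 and 9 points rest on assumed counts and show only the logic. That the Safety section will be close to one-armed rests on the expectation that events in non-users will be judged not related.

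The consequence is limited. SAP 6.3.1 treats everything outside the primary criterion as descriptive, the combined table could be built from Listing 16.2.7.1, and the primary conclusion is unaffected.

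**What to change.** In SAP section 11:

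- Add by-group tables of all treatment-emergent adverse events regardless of relationship: any event, and by SOC/PT, giving patients and events.
- State one treatment-emergent rule and apply it to all events, incidents included.
- Use the safety population of protocol 9.2, which is all included patients. This must be stated because SAP section 11 uses the Full Analysis Set, which SAP section 5 defines by use of the device. That definition is a separate point.
- Keep the incident and non-related tables as subsets, both under Safety.

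In SAP section 12, record any departure from protocol 9.5 that remains.

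A row for serious events of any relationship would be a useful optional addition, although the protocol does not clearly require it. The numbering mismatch (14.3.1.1 and 14.3.1.2 in the list, 14.3.1.3 and 14.3.1.4 in the mocks) is a separate editorial point.

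The cost is a few extra tables and some SAP wording. The data are already collected, and neither study conduct nor the primary analysis changes.

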12. CHANGES IN THE CONDUCT OF THE STUDY OR PLANNED ANALYSIS

The cold symptoms' duration was defined in the protocol as the number of symptomatic days between D1 and the first day the subject reports not having the symptom for two consecutive days.

Since several patients still reported having symptoms while they reported they did not feel sick anymore at the question 1 during the two last days of completion of the WURSS-K questionnaire, their positive answers to the cold symptoms' items have been considered as non-significant. Consequently, the question 1 has been taken into account instead of the corresponding items to determine the end of the cold symptoms' duration, however only on the condition that the two last days of completion were consecutive.

If the two last days of completion were not consecutive, positive answers to cold symptoms' items are still considered as symptomatic, even if the two last answers to the question 1 are negative. The symptom ends at the last symptomatic day if the patient reported the absence of this symptom after this day. Otherwise, the duration of the symptom is censored at D30 or at the end of the study, whichever occurs first.

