8.1.4 Secondary Endpoints

- **Duration of cold symptoms** (items 2 to 7) will be assessed by means of the WURSS-K (assessed once daily in the evening).

During treatment period, the WURSS-K will be assessed once daily in the evening, taking in account the symptoms from the morning to the evening.

After D10, the WURSS-K will be assessed once daily until the subject feels not sick for two consecutive days.

For each item, the duration is defined as the number of symptomatic days between D1 and the first day the subject reports not having the symptom for two consecutive days.

To be noticed that the duration may be censored at day 30.

- Number of subjects who develop respiratory complication requiring antibiotic prescription during a 20-day follow-up period. Healsea® Children is expected to reduce acute rhinitis complications.
- Frequency and number of days of use of concomitant treatments that may affect common cold symptoms (antibiotics, antipyretics, mucolytics, decongestants, antitussives, systemic and topical

Version: **2.0**; **08** Sep **2021** Page **30** of **61** Study Number: **LPH-2101**

corticosteroids). By reducing duration of common cold symptoms, Healsea® Children will very likely reduce the use of common rescue medication.

- Number of family members in close contact developing common cold symptoms after the patient all over the study period. The daily use of Healsea® Children started at the onset of common cold symptoms is expected to reduce relative's contamination.
- Safety: Assessment of adverse events/incidents/undesirable expected side effects throughout the study.

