8.3.2.3 Subject replacement

It is not anticipated to replace withdrawal patients.

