3. STUDY DESIGN

This is a prospective, open label, interventional, national (Poland), multicentric study. During this prospective interventional study, one cohort of IgE-dependent allergic children with early symptoms of infectious rhinitis will be followed, children being treated with Healsea® Children on top of common cold conventional therapies or with conventional therapies only (nasal irrigation excepted). This study aimed to confirm the benefit of Healsea® Children in a real life setting in children with perennial allergy.

Investigational plan description (see Figure 1):

- **Visit 1 (V1) – (Day 1): Screening/Inclusion**

Information and provision of the information sheet to legal guardians and participants, consent and assent signatures, demographic data and medical history, ongoing medication, physical and clinical examination, inclusion/non-inclusion criteria, record of patient choice regarding Healsea® Children use.

- **D1-D10 (at home):**

Daily completion of the electronic diary (WURSS-K, adverse events/incident/ undesirable expected side effects and concomitant medications, contamination of relatives if applicable, Healsea® Children daily administration if applicable).

– **D5±2 (at home): Telephone call 1**

Investigator/nurse call to review patient status and study progress, adverse event/incident/undesirable expected side effects and concomitant treatments.

– **Visit 2 (V2) – (Day 10±2): End of treatment**

End of Healsea® Children nasal spray treatment if applicable, assessment of symptoms, diary review, reporting of adverse events/incident/undesirable expected side effects.

– **D11-D30±5 (at home):**

Daily completion of the diary (Adverse event, concomitant medications, contamination of relatives if applicable, WURSS-K if applicable, until the subject feels not sick for two consecutive days).

– **D20±2 (at home): Telephone call 2**

Investigator/nurse call to review patient status and study progress, adverse events and concomitant treatments.

– **Visit 3 (V3) – (Day 30±5): End of study**

Physical and clinical examination, diary review, reporting of adverse events and concomitant treatments

The maximal study duration for each subject is 35 days.

Visit name	ACUTE PHASE				FOLLOW-UP		
	Screening/Inclusion	At home	Telephone call	End of treatment	At home	Telephone call	End of study
Visit Number	V1		TC1	V2		TC2	V3
Days/Weeks	D1	D1 – D10	D5±2	D10±2	D11 – D30±5	D20±2	D30 ± 5
Screening and General Assessments							

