4. SAMPLE SIZE

An arbitrary cohort of 200 children has been chosen. A cohort of 100-exposed and 100-not exposed patients is anticipated to allow to demonstrate the interest of using Healsea® Children in the allergic paediatric population.

Indeed, 100 patients by arms are enough to detect a Cohen's effect size of 0.4 with a power of 80% and a type I error of 5%. Cohen's effect size is defined as the standardized difference between AUC in groups. Following Cohen's methodology, 0.4 is an intermediate size between a small effect (0.2) and a medium effect (0.5) and is coherent with the expected result.

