6.3. Statistical/Analytical issues

6.3.1. Significance level

All statistical analyses will be performed at the 0.05 global significance level (type I error rate), using two-sided tests.

The statistical results are conclusive for the primary efficacy criterion.

All the other statistical results have to be considered within a descriptive perspective and not as inferential issues. No adjustment for Type I error is done. P-values of statistical tests will be provided for information only.

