10.2.2. Impact of the treatment chosen on the cold symptoms' duration

Hereinafter, the “recovery date” is the first day of two last days the patient answered to the WURSS-K questionnaire. The patient must have reported a negative answer to the question 1 (“not sick”) and the two last days must be consecutive. Otherwise, there is no “recovery date” for the patient.

For the items 2 to 7 of WURSS-K questionnaire, the duration of the corresponding symptom is defined as the duration between first symptomatic day and last symptomatic day.

Cold symptom's duration (days) = Last symptomatic day – first symptomatic day + 1

For a given symptom, a symptomatic day is a day the patient gave an answer other than negative to the corresponding question (“do not have this”). Missing answers will be imputed by the last observation carried forward (LOCF).

The considered symptomatic days are between D1 and either D30, or the end of the study, or the day before the recovery date, whichever occurs first. Symptomatic days from the recovery date will not be taken into account.

For each of the items 2 to 7 of the WURSS-K questionnaire, the origin date will be the date of the first symptomatic day.

The considered event is the end of the symptom.

For patients who reported a negative answer to the corresponding question on the last day they answered to it, or for patients with a recovery date, the event date will be the last symptomatic day before his/her last day of completion of the questionnaire, or before the recovery date if it exists.

Patients who did not report a negative answer to the corresponding question on the last day they answered to it, and without recovery date, will be censored at D30 or at the end of the study, and the censoring date will be the date of D30 or the reference end date, whichever occurs first.

For patients who never reported the presence of a given symptom (never ticked “a little bad”, “bad” or “very bad”), if they completed the questionnaire at D1, then their origin date will be D1, they will be censored at D1 and their corresponding duration will be zero, else they will have neither origin date nor censoring date and the corresponding duration will be missing.

For each of the items 2 to 7 of the WURSS-K questionnaire, the impact of the treatment chosen on the corresponding cold symptom' duration will be analysed by means of a Cox model. Subjects will be analysed on the FAS.

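### SAP 12 ends a cold symptom on the 'not sick' answer instead of the symptom's own item, a rule prompted by study diaries, and plans no analysis by the protocol definition

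*SAP*

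**What the plan says.** **Protocol.** Section 7.3 asks about the duration of each symptom. Section 8.1.4 measures it per item: "the duration is defined as the number of symptomatic days between D1 and the first day the subject reports not having the symptom", where the absence must last two consecutive days. It adds that durations may be censored at day 30. The WURSS-K is completed daily from D1 to D10 whatever the answers. After D10 it continues only until the child has felt not sick two days running, which is question 1 and not items 2 to 7.

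**SAP.** Section 12 reports that several children ticked symptoms while answering 'not sick' on their last two completed days. It says "their positive answers to the cold symptoms' items have been considered as non-significant" and lets question 1 decide the end of the symptom, provided those two days are consecutive. If they are not, the same ticks still count.

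Section 10.2.2 puts this into practice. The recovery date is the first of the two last completed days, when both are 'not sick' and consecutive. Ticks from that date onward are ignored. The child is an event: "or for patients with a recovery date, the event date will be the last symptomatic day before his/her last day of completion", or before the recovery date where there is one. A child with no recovery date whose item is still positive at the last answer is censored at D30 or the end of study, whichever comes first.

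Table 14.2.2.2 (FAS) is the only duration output, with a hazard ratio, confidence interval and Wald p-value per symptom. The per-protocol repeat in SAP 5 covers only the AUC analyses. SAP 6.3.1 makes every result other than the primary descriptive.

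**The concern.** Feeling 'not sick' with a runny nose is not a contradiction. Question 1 asks how sick the child feels today, while the items ask about each symptom since yesterday. Under the SAP rule, time to the end of a symptom becomes partly time to a global answer.

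The plan is also uneven about what a tick means. A tick on D9 or D10 that is set aside for duration still enters the primary AUC, which sums all 14 items (SAP 10.1). With a gap between the last two diary days, the same tick with the same two 'not sick' answers counts as symptomatic.

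The override works in one direction only: it removes late symptomatic days and turns a censored child into an event. The study is open label, the family chooses the treatment (Protocol 8.2), and faster recovery with the spray is expected (Protocol 6.1). If the groups differ in how readily they answer 'not sick', that difference could pass into the hazard ratios for six symptoms. The planned output gives no way to see it.

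**Working it through.** **1. The plan's own figure.** SAP 4 says "100 patients by arms are enough to detect a Cohen's effect size of 0.4 with a power of 80% and a type I error". With two-sided alpha 0.05, n per arm = 2 × (1.960 + 0.842)² / 0.4² = 98.1, so 99. Power at 100 per arm is Φ(0.4 × √50 − 1.960) = Φ(0.868) = 80.7% (80.4% with the exact t distribution). The figure reproduces. It is set on the AUC, so this point does not affect it.

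**2. The same diary under both definitions.**

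| Diary | SAP 10.2.2 | Protocol 8.1.4 |
|---|---|---|
| A: symptom D1–D10, 'not sick' D9 and D10 | Recovery date D9; 8 − 1 + 1 = 8 days, event | Never two symptom-free days; censored at D10 (last diary day) or D30 |
| B: symptom D1–D14, 'not sick' D13 and D14 | Recovery date D13; 12 days, event | Censored at D14 or D30 |
| C: symptom D1–D3 and D7 only, no override | 7 − 1 + 1 = 7 days, event | 3 days, event |

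A and B show the override. At most two diary days of ticks are dropped, but event status changes. C shows a separate difference: SAP 10.2.2 spans from first to last symptomatic day, while the protocol counts from D1 to the first two symptom-free days. The two analyses therefore differ by more than the override.

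**3. Illustrative simulation, no true difference.** Every input here except 100 children per arm is an assumption. There were 300 trials. Symptom duration was Weibull (shape 1.8, mean about 9 days), identical in both arms. A share of children said 'not sick' 2 to 6 days before the symptom ended. The diary ran to D10 or to two days after feeling not sick, whichever was later. Analysis was by Cox model with Efron ties. HR above 1 means faster resolution with the device; the two-sided 5% rejection rate is in brackets.

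| Early 'not sick', control / device | Item still ticked on last diary day, control / device | SAP rule | Protocol rule, censored at last diary day | Protocol rule, censored at D30 |
|---|---|---|---|---|
| 0% / 0% | 0% / 0% | 1.00 (4.3%) | 1.00 (4.3%) | 1.00 (4.3%) |
| 20% / 20% | 8.6% / 9.1% | 1.01 (4.0%) | 1.00 (2.3%) | 0.99 (3.7%) |
| 10% / 30% | 4.5% / 13.6% | 1.06 (7.7%) | 0.89 (14.0%) | 0.78 (38.7%) |
| 20% / 40% | 8.8% / 17.6% | 1.08 (8.7%) | 0.90 (9.7%) | 0.81 (27.7%) |
| 20% / 60% | 9.1% / 26.4% | 1.17 (17.0%) | 0.80 (27.7%) | 0.67 (68.7%) |

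**4. A second set-up.** Here the mean duration was 7.7 days and 'not sick' was scattered around symptom end with SD 2 days (400 trials). Moving 'not sick' 1 day earlier in the device arm gave HR 1.04 (SAP) against 0.91 (item rule, last diary day). Moving it 2 days gave 1.13 against 0.86.

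**5. Reading.** With equal answering in both groups, every rule gives about 1. With unequal answering, the rules move in opposite directions. In every unequal scenario the item rule lies further from 1 than the SAP rule: for 20% against 40%, |ln 0.90| = 0.105 against ln 1.08 = 0.077.

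**The case against.** The defence is substantial. The change is disclosed in full. Duration is a secondary, descriptive endpoint, the primary AUC still uses every reported item, and Listing 16.2.6.1 holds the raw answers. The override is narrow: it needs 'not sick' on both of the last two completed days, which must be consecutive. A child with a complete diary who says 'not sick' from D5 to D10 keeps the ticks on D5 to D8.

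The root of the problem is in the protocol, which stops the diary on question 1 while defining duration by item. The SAP rule at least matches that stopping rule. The item rule must censor children who stopped recording because they felt well, and such censoring may be informative.

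All of this stands, and it limits the point. It does not supply the missing analysis or the missing count.

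A reader might infer more than the documents support:
- **That the rule was chosen after looking at results by group, or after database lock.** SAP 12 speaks only of several patients, without a group split or a date. Protocol 10.3 foresees a review meeting before lock that also validates the SAP. Open label means treatment could be known, not that it was used.
- **That the protocol rule should become the main analysis because it is nearer the truth.** The simulations do not support this. Protocol 8.1.4 also mentions censoring at day 30, so censoring at the last diary day is an added choice.

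**Conclusion.** The point holds in limited form. The documents show that answers already recorded in the study prompted a change in how symptom duration ends, that the change turns censored children into events, and that the planned output contains neither the protocol definition nor the number of children affected.

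The size is unknown, because the documents give no count and no split by group. If 'not sick' answering is similar in the two groups, the effect on the hazard ratio is negligible. If it differs, the assumed scenarios give 1.04 to 1.17 under the SAP rule and 0.91 to 0.67 under the item rule, with no true difference. The choice of rule could then decide the apparent direction.

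A reader might also infer that the two rules bracket the true hazard ratio. They do so in these set-ups, where the true ratio is 1, but that is not a general property. The primary conclusion and the sample size are unaffected. This is worth correcting because it is cheap and shows whether the duration result depends on the post hoc rule.

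**What to change.** 1. In SAP 10.2.2 and 12, label the question-1 rule as post hoc.
2. Add to Table 14.2.2.2, as a sensitivity analysis, the item-level definition of Protocol 8.1.4. Censor children whose item is still positive at the last completed diary day and, separately, at D30 or end of study.
3. Report by group and symptom how many children are overridden.
4. Describe a difference in duration as robust only if the analyses agree in direction.
5. Footnote that the two definitions also differ in origin and in how relapses are counted (diary C), so that a discrepancy is not put down to the override alone.

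The cost is one extra derivation from diary data already held, and a longer table. The added analysis will have more censoring, which may be informative, so it should be read as a check on the SAP rule and not as a replacement for it.
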